5.0 Participant Disposition

A summary of participant accountability by country and investigator will be provided where the number of participants in each of the following categories will be tabulated for each treatment group for the Intent-to-Treat Analysis Set:

ABBV-552
M23-515 – Statistical Analysis Plan
Version 3 – 20 September 2024

- Participants randomized in the study;
- Participants who took at least one dose of study treatment;
- Participants who completed study treatment;
- Participants who prematurely discontinued study treatment;
- Participants in each analysis population, as applicable.

The summary of participant accountability by investigator also will include the number of participants who screened and the number of participants who screen failed and will be summarized for all participants.

[figure not shown]
The number and percentage of participants in the safety analysis set who prematurely discontinued study treatment will be summarized by reason for not completing study treatment overall and by treatment group.

The number and percentage of participants in the safety analysis set who did not complete the protocol defined follow-up period will be summarized by reason for not completing study overall and by treatment group.

6.0 Study Treatment Duration and Compliance

For the safety analysis set, duration of treatment will be summarized for each treatment group and for total ABBV-552 group. Duration of treatment is defined for each Participant as last dose date minus first dose date + 1. Duration of treatment will be summarized using the number of participants treated, mean, standard deviation, median, minimum and maximum. In addition, the number and percentage of participants in each treatment duration interval (1 to 28, 29 to 56, 57 to 84, > 84) will be summarized.

Treatment compliance will be summarized for the entire treatment period by treatment group and total ABBV-552 group for the safety analysis set. Treatment compliance is defined as the number of capsules actually taken divided by the number of capsules that should have been taken (number of capsules that should have been taken equals 2 per day multiplied by days where participant is on study treatment regardless of treatment

interruption). Percent compliance will be summarized with mean, SD, median, min, and max, as well as categorically (< 80%, $\ge 80\%$ to $\le 120\%$, > 120%).

7.0 Participant Characteristics

Categorical variables will be summarized with the number and percentage of participants. Continuous variables will be summarized with descriptive statistics (number of non-missing observations, mean and standard deviation, median, minimum and maximum).

[figure not shown]
7.1 Demographics and Baseline Characteristics

Demographics and baseline or disease characteristics will be summarized descriptively, overall and by treatment group for the safety analysis set. Unless otherwise specified, baseline is defined as the last non-missing value prior to the first administration of study treatment.

Continuous demographic variables include age, weight, height, and body mass index (BMI).

Categorical demographic variables include:

- Sex
- Ethnicity
- Race
- Age $(<65, \ge 65 <75, \ge 75 <85, \ge 85)$
- Weight ($< 60 \text{ or } \ge 60 \text{ kg}$) by sex
- BMI ($< 25 \text{ or } \ge 25 \text{ kg/m}^2$) by sex
- Region (Europe, North America, or rest of world)
- Nicotine user (current, former, never, unknown)
- Alcohol user (current, former, never, unknown).

Disease characteristics include the time since symptom (cognitive impairment) onset and time since Alzheimer's disease diagnosis. This will be summarized in years as a continuous variable.

[figure not shown]
The history of symptomatic treatment for AD will be summarized categorically as: previously treated and stopped, previously treated and treatment is ongoing, and never treated. For those who were previously treated and stopped, the reason for discontinuation will be summarized.

The following will be summarized for the mITT analysis set. The number and percentage of participants on symptomatic treatment for AD as reported on the concomitant medication eCRF at baseline will be summarized. The number of participants that start, stop or change doses of symptomatic treatment for AD during the treatment will be summarized.

7.2 Medical History and Prior and Concomitant Medications

Medical history data will be coded using the Medical Dictionary for Regulatory Activities (MedDRA). The actual version of the MedDRA coding dictionary will be noted in the statistical tables and clinical study report. The number and percentage of participants in each medical history category (by MedDRA system organ class (SOC) and preferred term) will be summarized overall, all active treatment, and by treatment group for the safety analysis set. The SOC will be presented in alphabetical order, and the preferred terms will be presented in alphabetical order within each SOC. Participants reporting more than one condition/diagnosis will be counted only once in each row (SOC or preferred term).

Prior and concomitant medications will be summarized separately. The number and percentage of participants taking prior and concomitant medications will be summarized by generic drug name, based on the World Health Organization (WHO) Drug Dictionary overall, all active treatment, and by treatment group for the safety analysis set. The actual

version of the WHO Drug Dictionary will be noted in the statistical tables and clinical study report.

7.3 Protocol Deviations

For each of the following protocol deviation categories and across all categories, the number and percentage of randomized participants with at least one protocol deviation will be summarized overall, all active treatment, and by treatment group for the safety analysis set:

- Participant entered into the study even though did not satisfy entry criteria;
- Participant developed withdrawal criteria during the study but was not withdrawn;
- Participant received wrong treatment or incorrect dose of study treatment;
- Participant took prohibited concomitant medication.

A listing of participants with protocol deviations will be provided.

8.0 Handling of Potential Intercurrent Events for the Primary Endpoint

The primary efficacy endpoint of change from baseline in the ADAS-Cog 14 score (defined in Section 3.1) will be analyzed based on the mITT analysis set and the following methods will be used to address potential intercurrent events:

- Efficacy data which is missing due to a participant's discontinuation from the study, or blind broken will be assumed missing at random and will not be included in the statistical analyses.
- Efficacy data collected after a start, stop or dose change of AD medication during the study will not be included in the primary analysis and will be assumed missing at random.

9.0 Efficacy Analyses

9.1 General Considerations

Unless otherwise noted, all efficacy analyses will be conducted on the mITT analysis set.

The primary analysis will be conducted following a database lock after all participants have completed Visit 11 (Week 12) or prematurely discontinued study drug.

Where hypothesis testing is specified, it will be based on a 2-sided $\alpha = 0.1$ level.

Continuous variables will be analyzed using mixed-effects model for repeated measures (MMRM) method or analysis of covariance (ANCOVA) as noted. For continuous variables analyzed using an MMRM or ANCOVA, summary statistics by visit will also be provided by treatment group.

For analyses that include the stratification factor in the model (on symptomatic treatment for AD at baseline – yes or no), any participant who is randomized within an incorrect stratum will be analyzed according to the actual stratum to which the participant belongs according to the concomitant medication eCRF, unless otherwise indicated.

9.2 Handling of Missing Data

Missing data for the primary endpoint and the continuous analysis of other efficacy endpoints that are measured at multiple time points post-baseline will be addressed in a model-based fashion via an MMRM analysis with no data imputation prior to creating the model.

Efficacy data collected after a start, stop or dose change of AD medication during the study will not be included in the primary, secondary, or additional efficacy analyses and will be assumed missing at random unless otherwise noted.

For continuous efficacy endpoints measured at one time point post-baseline, missing data will not be imputed, unless otherwise noted.

9.3 Primary Efficacy Endpoint and Analyses

9.3.1 Primary Efficacy Endpoint

The primary efficacy endpoint is the change from Baseline in the ADAS-Cog 14 total score at Week 12.

[figure not shown]
9.3.2 Main Analysis of Primary Efficacy Endpoint

The attributes of the estimand corresponding to the primary efficacy objective are summarized in Table 1.

Table 1. Summary of the Estimand Attributes Corresponding to the Primary Efficacy Objective

	Attributes of the Estimand				
Estimand Label	Treatment	Endpoint	Population	Handling of Intercurrent Events	Statistical Summary
Primary estimand	Placebo, ABBV-552 1 mg, 5 mg, and 15 mg QD	Change from Baseline in ADAS-Cog 14 score at Week 12	mild Alzheimer's Disease participants	Efficacy data which is missing due to a participant's discontinuation from the study will be assumed missing at random and will not be included in the statistical analyses. Efficacy data collected after a start, stop or dose change of AD medication during the study will not be included in the primary analysis and will be assumed missing at random	LS mean difference between each ABBV-552 dose and placebo in ADAS-Cog 14 score change from baseline at Week 12 based on an MMRM

The primary analysis of change from baseline in the ADAS-Cog 14 score will be conducted using an MMRM including treatment group, visit, treatment-by-visit interaction, and the randomization stratum as fixed effects and the baseline ADAS-Cog 14 score as a covariate. The unstructured covariance structure will be used to estimate the

within-participant variance-covariance. Denominator degrees of freedom will be computed using the Kenward-Roger method. The primary comparison time point is Week 12, and the group mean treatment difference between each dose and placebo at Week 12 will be based on contrasts from this model. If the model fails to converge with an unstructured covariance structure, the compound symmetry (CS) covariance structure will be substituted. If the model still fails to converge, data will be analyzed as observed using an ANCOVA with treatment and the randomization stratum as fixed effects and baseline ADAS-Cog 14 score as a covariate.

P-value for testing the group mean difference between each dose and placebo groups will be calculated.

[figure not shown]

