7.4 Statistical Analyses for Efficacy

Analysis of the primary and all other efficacy endpoints will be conducted on the mITT analysis set based on 2-sided α = 0.1 level, unless otherwise specified in the SAP.

Summary and Analysis of the Primary Endpoint

The primary analysis of ADAS-Cog 14 will be conducted using an MMRM including treatment group, visit, treatment-by-visit interaction, and the randomization stratum as fixed effects and the baseline ADAS-

Cog 14 score as a covariate. The unstructured covariance structure will be used to estimate the within participant variance-covariance. Denominator degrees of freedom will be computed using the Kenward-Roger method. The group mean treatment difference between each dose and placebo at Week 12 will be based on contrasts from this model.

Summary and Analysis of Additional Efficacy Endpoint

The following analyses will generally apply unless otherwise noted in the SAP. For continuous efficacy endpoints, the mean, standard deviation, median, minimum, and maximum will be reported for each treatment group. For endpoints measured at a single post-baseline time point, the between-group treatment summary will be based on an analysis of covariance (ANCOVA) including treatment group, randomization stratum, and baseline for that respective parameter. For endpoints measured at multiple post-baseline time points, the between-group treatment summary at each visit will be conducted using an MMRM including treatment group, visit, treatment-by-visit interaction, and the randomization stratum as fixed effects and the baseline values associated with the endpoint as a covariate. Missing data will not be imputed before performing the MMRM.

Subgroup Analysis for Efficacy

Subgroup analyses of the primary endpoint will be conducted for the following subgroups.

- On symptomatic treatment for AD at baseline: Yes, No
- Sex
- Age: < 65 years or ≥ 65 years and < 75 years or ≥ 75 years

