2.3 Treatment Assignment and Blinding

Participants will be randomized to placebo, ABBV-552 1 mg QD, ABBV-552 5 mg QD, or ABBV-552 15 mg QD, in a 1:1:1:1 ratio. Randomization will be stratified by whether or not the participant is currently receiving a stable dose of symptomatic treatment for AD at Baseline/Day 1.

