2.4 Sample Size Determination

It is assumed that the treatment difference of Alzheimer's Disease Assessment Scale-Cognitive Subscale (ADAS-Cog) 14-item score change from Baseline at Week 12

between each ABBV-552 treatment arm and placebo is 2.85 with a pooled standard deviation of 5.7 (effect size of 0.5) based on data from prior cholinesterase inhibitor and AbbVie studies. The standard deviation of 5.7 was estimated from pooled previous AbbVie symptomatic treatment in mild/moderate AD studies (M10-984, M10-985, M10-822, and M12-033). Assuming a 20% discontinuation rate, 60 participants randomized per group will provide about 80% power to detect the above treatment difference in ADAS-Cog 14 score at the 2-sided 10% significance level. East version 6.5.3 was used for the sample size calculation.

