9.4.3 Cogstate Brief Battery (CBB) and International Shopping List Test (ISLT)

The CBB consists of the following components: detection test [DET], identification test [IDN], one card learning [OCL], and one back test [ONB]. The ISLT consists of the following: ISLT-Immediate Recall and ISLT-Delayed Recall. Together, the CBB and ISLT are referred to as the Cogstate Computerized Battery (CCB).

The change from baseline for the CCB will be analyzed using an MMRM including treatment group, visit, treatment-by-visit interaction, and the randomization stratum as fixed effects and the baseline score as a covariate. The unstructured covariance structure will be used to estimate the within-participant variance-covariance. Denominator degrees of freedom will be computed using the Kenward-Roger method. The group mean treatment difference between each dose and placebo at Weeks 1, 2, 6, and 12 will be based on contrasts from this model. If the model fails to converge with an unstructured covariance structure, the compound symmetry (CS) covariance structure will be substituted. If the model still fails to converge, data will be analyzed as observed using an ANCOVA model with treatment and the randomization stratum as main effects and the baseline of the measure being analyzed as a covariate.

This will be calculated for the primary outcome measures (e.g., reaction time, accuracy, correct responses) for each component of the CCB as well as the global and domain-specific (attention domain, learning/working memory, and episodic memory) composite scores. The primary outcome measures and calculation details of the composite scores may be found in Appendix C.

Additionally, the effect sizes for the change from baseline for each component of the CCB will be calculated at Weeks 1, 2, 6 and 12.

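### The primary MMRM has no baseline-by-visit term, so one baseline ADAS-Cog 14 slope serves Week 6 and Week 12; the cost is small and conditional, and one added parameter removes it

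*SAP*

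**What the plan says.** SAP 9.3.2 specifies the primary MMRM with treatment, visit, their interaction and the stratum as "fixed effects and the baseline ADAS-Cog 14 score as a covariate", with unstructured covariance and Kenward-Roger degrees of freedom. The paragraph on the primary endpoint in Protocol 7.4 matches it. Treatment is the only term crossed with visit.

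ADAS-Cog 14 is scheduled after baseline at Week 6 and Week 12 (Protocol Appendix D), and SAP 9.3.3.2 takes the Week 6 contrast from the same model. The model therefore has two visits and one baseline slope.

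The same form is used for other repeatedly measured endpoints. Protocol 7.4 includes "the baseline values associated with the endpoint as a covariate", and SAP 9.4.3 (Cogstate) has "the randomization stratum as fixed effects and the baseline score as a covariate". Neither document contains a baseline-by-visit term.

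On missing data, SAP 8.0 and 9.3.2 assume missing at random for participants who discontinue the study and for data set aside after a change in AD medication. The sample size section (SAP 2.4) states: "Assuming a 20% discontinuation rate, 60 participants randomized per group will provide about 80% power".

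**The concern.** Change from baseline may relate to baseline score differently at Week 12 than at Week 6. A common slope is then a compromise that fits neither visit exactly. An unstructured covariance matrix does not repair a mean model that is wrong.

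Two things could follow at the primary time point. Residual variance at Week 12 would be larger than necessary. Also, if the participants who still have a Week 12 score differ in baseline between arms, a wrong slope would not fully correct for that difference and the contrast would shift. With a planned 20% discontinuation rate handled by likelihood, the mean model carries some of the burden of the missing-data handling.

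**Working it through.** **Reproducing the plan's power.** The inputs from SAP 2.4 are a difference of 2.85, SD 5.7, two-sided 10% level, 60 per arm and 20% loss. SAP 2.3 gives equal allocation.

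- Evaluable per arm: 60 × 0.8 = 48.
- SE = 5.7 × √(2/48) = 1.163.
- Power = Φ(2.85/1.163 − 1.645) = Φ(0.805) = 78.9% (78.4% with the noncentral t).

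This agrees with the stated figure of about 80%.

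**How the common slope is formed.** With complete data at two visits, the generalised least squares weight on the Week 6 slope is

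w6 = (s12² − ρ·s6·s12) / (s6² + s12² − 2ρ·s6·s12).

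Only s12 = 5.7 is in the documents. Assuming s6 = 5.0 and ρ = 0.55, w6 = (32.49 − 15.675)/(25 + 32.49 − 31.35) = 16.815/26.14 = 64%. With s6 = s12 it is 50% at any ρ.

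**Simulation.** Four arms of 60 were simulated with about 20% missing at Week 12, using a two-visit unstructured MMRM fitted by maximum likelihood rather than Kenward-Roger. There were 1,000 to 1,500 trials per scenario. The assumptions not found in the documents are:

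- baseline SD 6 to 10;
- visit correlation 0.3 to 0.7;
- slopes of change on baseline from −0.2 to +0.1;
- log-odds of missingness 0.8 per baseline SD where loss depends on baseline.

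The one-arm row below used Week 6 SD 5.0, correlation 0.55, baseline SD 8, and slopes −0.05/−0.15 and 0/−0.2. The gap is the difference between the Week 6 and Week 12 slopes. Bias is shown as absolute size, because its sign depends on the direction of the slope gap and of the loss.

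| Dependence of loss on baseline | Bias, gap 0.1 | Bias, gap 0.2 |
|---|---|---|
| Same in all arms | at most 0.055, the same in both models | at most 0.03 |
| Active arms only | 0.05 to 0.12 | 0.11 to 0.24 |
| One arm only | 0.14 (0.02 with interaction) | 0.24 (0.02 with interaction) |
| Opposite in placebo and 15 mg | 0.17 to 0.29 | 0.33 to 0.49 |

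The Monte Carlo standard error is about 1.15/√1500 = 0.03. A repeat of the one-arm case gave about 0.10 (gap 0.1) and 0.21 (gap 0.2). Letting half the losses fall before Week 6, and so outside mITT, gave 0.22 against 0.02 with the interaction (gap 0.2).

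With baseline-by-visit in the model, bias for gaps of 0.1 and 0.2 stayed within about 0.07 of zero. At a gap of 0.3, opposite dependence gave 0.60 against 0.04. The active-only scenario gave −0.17 against +0.11, so residual noise of about 0.1 should be kept in mind.

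**Precision.** With equal slopes and 20% random missingness the two models gave the same SE (1.135). For gaps of 0.1 to 0.2 with equal dependence the common-slope SE was 0.3% to 3% larger, which in variance terms is 1.003² − 1 = 0.6% to 1.03² − 1 = 6.1%. In some differential-loss scenarios the increase was nil. On the plan's own formula, a 2% larger SE gives Φ(2.4495/1.02 − 1.645) = 77.5%, and a 3% larger SE gives Φ(2.4495/1.03 − 1.645) = 76.8%, against 78.9%.

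**Effect on the test.** Taking SE 1.15, a bias of 0.25 is 0.22 SE. Null rejection is then Φ(−1.645 + 0.22) + Φ(−1.645 − 0.22) ≈ 10.8% at nominal 10%. A bias of 0.5 (0.43 SE) gives about 13.2%. In the opposite-dependence simulations the observed rates were 10.1% to 11.3% (gap 0.1) and 10.9% to 13.6% (gap 0.2), against 9.3% to 11.1% with the interaction.

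**The case against.** The protocol and SAP agree on a prespecified model, so there is no documentary error. The study is declared hypothesis-generating, with no type I error control (Protocol 7.7, SAP 13.0). Bias needs two conditions together, and the documents give no evidence for either. Twenty per cent discontinuation need not mean that 20% of mITT lack a Week 12 score: mITT requires a post-baseline ADAS-Cog 14, and the premature discontinuation visit shares the Week 12 column in Appendix D. The copy-reference analysis ends in an ANCOVA that, fitted at Week 12, has its own slope. All of this stands, and it keeps the point minor. The copy-reference analysis is only a partial check, however, because it also changes the missing-data assumption. The other two sensitivity analyses reuse the primary MMRM.

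A reader might infer more than the documents support:

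- *That baseline-dependent missingness alone biases the contrast.* It does not. When the dependence is equal across arms the error cancels, even with unequal slopes.
- *That the missing-at-random assumption fails.* Missing at random describes the missingness mechanism given the observed data. A mis-specified mean can harm the estimate without making that assumption false.
- *That Week 6 dominates the common slope, so Week 12 takes most of the error.* The 64% weight rests on an assumed Week 6 SD. With equal SDs the split is even.

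**Conclusion.** The point holds as a minor specification weakness. The primary MMRM imposes one baseline slope on two visits. If the slopes are equal, this costs nothing measurable. If they differ by 0.1 to 0.2, the Week 12 variance is about 0 to 6% larger, worth at most about two points of power.

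If, in addition, the dependence of loss on baseline differs between arms, bias is about 0.1 to 0.25 points when one arm differs (4% to 9% of 2.85). It reaches up to about 0.5 points (18%) when placebo and a dose arm have opposite dependence.

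These sizes depend on an assumed Week 6 SD, visit correlation, slopes, baseline SD and loss pattern. The documents fix only the Week 12 SD, the effect, the sample size and the overall discontinuation rate. They do not support a claim that the primary analysis is invalid or that the stated power is wrong.

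**What to change.** In SAP 9.3.2, add the baseline ADAS-Cog 14-by-visit interaction to the fixed effects of the primary MMRM. The change should be made before unblinding. SAP 12.0 plans an unblinded interim analysis that uses Week 6 ADAS-Cog 14, so the cleanest time is before that. SAP 14.1 currently reports no changes from the protocol and should record the departure from Protocol 7.4.

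The cost is one extra parameter, no new data, one added model term and one entry in 14.1. The two sensitivity analyses that reuse the primary MMRM would inherit the term.

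Stratum-by-visit, and the same change in SAP 9.4.3 (Cogstate, four visits) and 9.5 (subgroups), are optional. They were not evaluated, and in the smaller subgroup fits extra terms draw on limited data.

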9.5 Efficacy Subgroup Analyses

The primary endpoint will be conducted for the following subsets of participants. Within each subgroup category, data will be divided into mutually exclusive subsets and then a separate analysis will be performed for each subset (e.g., for the "Sex" category, a separate analysis will be performed for all male participants and the same analysis will be performed for all female participants.)

- On symptomatic treatment for AD at baseline: Yes, No
- Sex
- Age: < 65 years or ≥ 65 years and < 75 years or ≥ 75 years

Other subgroup analyses (e.g., subgroups based on biomarkers) may be conducted given sufficient data.

The MMRM will include treatment group, visit, treatment-by-visit interaction, and the randomization stratum (for the age and sex subgroups only) as fixed effects and the baseline ADAS-Cog 14 score as a covariate. The unstructured covariance structure will be used to estimate the within-participant variance-covariance. Denominator degrees of freedom will be computed using the Kenward-Roger method. The group mean treatment difference between each dose and placebo at Week 12 will be based on contrasts from this model. If the model fails to converge with an unstructured covariance structure, the compound symmetry covariance structure will be substituted. If the model still fails to converge, descriptive statistics based on the univariate summaries will be provided.

[figure not shown]

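### The convergence fallback to plain compound symmetry gives wrong per-visit standard errors whenever visit variances differ; this matters mainly for the four-visit Cogstate models and only if the fallback is used

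*SAP*

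**What the plan says.** SAP 9.3.2 fits an "MMRM including treatment group, visit, treatment-by-visit interaction, and the randomization stratum as fixed effects and the baseline ADAS-Cog 14 score as a covariate". The first-choice covariance is unstructured ("The unstructured covariance structure will be used to estimate the" within-participant covariance), and "Denominator degrees of freedom will be computed using the Kenward-Roger method". The contrast of interest is fixed: "The primary comparison time point is Week 12".

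On non-convergence, "the compound symmetry (CS) covariance structure will be substituted". The last step is: "If the model still fails to converge, data will be analyzed as observed using an ANCOVA with treatment and the randomization stratum as fixed effects", with baseline score as covariate.

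SAP 9.4.3 applies the same sequence to the Cogstate models at Weeks 1, 2, 6 and 12: "If the model fails to converge with an unstructured covariance structure, the compound symmetry (CS) covariance structure will be substituted". It also ends in an ANCOVA. SAP 9.5 applies it to the subgroup ADAS-Cog models ("the compound symmetry covariance structure will be substituted"), but its last step is descriptive statistics.

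No section names a heterogeneous structure or an empirical (sandwich) standard error. Protocol 7.4 specifies unstructured covariance for the primary model and gives no fallback.

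**The concern.** Unstructured covariance is chosen so that equal variances and equal correlations need not be assumed. On failure, the rule moves from the least restrictive structure to one of the most restrictive and skips the structures in between that keep a separate variance for each visit. Kenward-Roger is a small-sample adjustment and does not repair a wrong covariance structure. If variance changes over time, the pooled variance is wrong at individual visits, and a test labelled 10% two-sided (SAP 9.1) no longer runs at 10%. The MMRM sensitivity analyses in SAP 9.3.3.1 and the Week 6 contrast in 9.3.3.2 reuse the primary model and so inherit the rule. A repair chosen after a model had failed would be a data-driven change, so the place to settle it is the SAP.

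**Working it through.** **Inputs from the documents.** Difference 2.85, SD 5.7, 60 randomized per arm, 20% discontinuation (SAP 2.4), so 48 evaluable; two-sided level 0.10 (SAP 9.1). ADAS-Cog 14 has two scheduled post-baseline visits, Weeks 6 and 12, and Cogstate has four (Protocol Appendix D).

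**Assumed.** All SDs other than 5.7 at Week 12 for ADAS-Cog 14. The documents give none by visit.

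**The plan's own figure.** SE = 5.7 × √(2/48) = 1.164. Power = Φ(2.85/1.164 − 1.645) = 78.9% (78.4% with the noncentral t), consistent with the stated 80% or so.

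**Covariance parameters.** Unstructured needs 2 × 3/2 = 3 for two visits and 4 × 5/2 = 10 for four. With two visits, heterogeneous compound symmetry has two variances and one correlation, which is the unstructured model reparameterised.

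**Two visits, complete data, leaving aside the baseline and stratum terms.** With treatment-by-visit in the model, compound symmetry and unstructured give the same Week 12 contrast, but the compound-symmetry variance is the average of the two visit variances:

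- SE ratio = √((s₆² + 5.7²)/2) / 5.7
- actual level = 2 × (1 − Φ(1.645 × ratio))

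| Week 6 SD (assumed) | SE ratio at Week 12 | Actual level |
|---|---|---|
| 5.3 | 0.966 | 11.2% |
| 5.0 | 0.941 | 12.2% |
| 4.5 | 0.901 | 13.8% |
| 4.0 | 0.864 | 15.5% |
| 5.7 (equal) | 1.000 | 10.0% |
| 6.84 (1.2 times) | 1.105 | 6.9% |

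**With dropout.** REML simulations used 4 × 60 participants, about 20% of Week 12 values missing at random given Week 6, and correlation 0.6. The mean compound-symmetry SE divided by the mean unstructured SE was 0.94, 0.89 and 0.84 for Week 6/Week 12 SD ratios of 0.9, 0.8 and 0.7, implying levels of about 12%, 14% and 17%. With equal SDs both mean SEs were 1.115. The simulations had no baseline or stratum terms and used a t reference with 190 df instead of Kenward-Roger.

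**Four Cogstate visits, complete data.** Assume SDs of 4.5, 4.8, 5.2 and 5.7 at Weeks 1, 2, 6 and 12; only their ratios matter. The pooled variance is (20.25 + 23.04 + 27.04 + 32.49)/4 = 25.705, so the pooled SD is 5.07.

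| Visit | 5.07 / visit SD | Actual level |
|---|---|---|
| Week 1 | 1.127 | about 6% |
| Week 2 | 1.056 | about 8% |
| Week 6 | 0.975 | about 11% |
| Week 12 | 0.889 | about 14% |

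**How often the fallback would be used.** In two-visit simulations at 60 per arm, the unstructured fit failed in 0 of 2,250 trials. A further check that included baseline and stratum, with about 20% dropout and correlation 0.6, gave 0 of 200 failures for four visits at 60 per arm, 0 of 200 for four visits at 30 per arm, and 0 of 200 for two visits at 6 per arm. These used a general-purpose optimiser, not the SAS algorithm, so they are indicative only.

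**The case against.** The strongest objection is that the rule will rarely, if ever, apply. The primary model has three covariance parameters and about 240 participants, the subgroup models also have only two visits, and no simulated fit failed, even with four visits. This stands, and it limits the practical weight of the point. It does not make the fallback valid in the case it is written for, and Cogstate gives it the most opportunities: ten parameters, fitted to six tests plus global and domain composites.

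The direction of the error is also open. A reader might infer that the fallback always inflates the false-positive rate, or that the primary Week 12 test does not hold its 10% level. The documents support neither. They give no visit-specific SDs: with flat variance there is no error, with falling variance the Week 12 test is conservative, and as planned the primary test uses unstructured covariance. SAP 9.4.3 takes contrasts at all four visits without singling out Week 12, so growing variance would make its early tests conservative and its later ones liberal.

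Trying compound symmetry before ANCOVA is a defensible choice for the primary model, because it keeps participants seen only at Week 6. That stands too, and it makes any change in 9.3.2 a trade-off.

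The primary endpoint has partial cover. The copy-reference analysis in SAP 9.3.3.1 applies ANCOVA to each imputed dataset and does not depend on the MMRM converging.

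Finally, Protocol 7.7 and SAP 13.0 disclaim type I error control across doses and endpoints. This lowers the stakes, but each individual test is still presented as a 10% test.

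**Conclusion.** The point holds conditionally and is minor. If the fallback is triggered and visit variances differ, the per-visit standard errors are wrong in a predictable direction. Under the assumed SDs, the ADAS-Cog Week 12 level ranges from 6.9% to 15.5%, and the Cogstate levels from about 6% to 14% depending on visit. These figures rest on assumed SDs, complete data and a simplified mean model; the two-visit simulations with dropout agree in direction and approximate size. If the fallback is never used, or variances are equal across visits, the effect is nil. It is unlikely to be used in the two-visit models. A reader might infer that Cogstate non-convergence is to be expected; neither the documents nor the simulations show that. The case for changing the text is that a valid fallback costs almost nothing to specify in advance.

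**What to change.** **Main change, SAP 9.4.3 (Cogstate).** After unstructured, try heterogeneous Toeplitz (4 variances + 3 correlations = 7 parameters), then heterogeneous compound symmetry (4 + 1 = 5), before any homogeneous structure. Both keep a separate variance for each visit.

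**Optional, SAP 9.3.2 (primary).** A heterogeneous step adds nothing with two visits. Choose one of two routes:

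- Keep compound symmetry, with empirical (sandwich) standard errors and a stated degrees-of-freedom method compatible with them in place of Kenward-Roger.
- Go directly to the Week 12 ANCOVA already listed there, which uses only the Week 12 variance, and accept the loss of participants seen only at Week 6.

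**SAP 9.5 (subgroups).** The last step listed is descriptive statistics. If the ANCOVA route is wanted here, an ANCOVA has to be added; deleting the compound-symmetry step alone would leave no model-based comparison.

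**Cost.** A few sentences of SAP text and slightly more programming.
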